Those members of the research team (principal investigator, co-investigators, study staff) who consent patients have been trained in informed consent procedures, are familiar with the protocol, and are listed as a consenter in the application document. Patients are given adequate time and privacy to consider the research study. Before the patient signs the consent, the consenter must be satisfied that the participant understands the information provided, has had an opportunity to discuss the information and ask questions, and is aware that he/she may withdraw from the study at any time. We will not be enrolling Non-English speaking participants to this study.

STUDY IMPLEMENTATION: We will use stratified randomization to assign enrolled patients 1:1:1 to the 3 study arms using a random number generator with the condition concealed until randomization. Patients and their clinicians will be informed of the condition to which the patient was assigned after randomization. The SCP template will be completed via EPIC or in paper format. The EPIC templates have been developed and created in EPIC with the guidance of the clinical co-investigators and the clinic staff. Currently, we are working with clinic staff to test the EPIC templates and then to work with the EPIC programming team make necessary modifications for staff and patient utility. The SCP that has been built into EPIC is based on the template developed by the American Society of Clinical Oncology (ASCO) via a multi-stakeholder process. This ASCO template has been revised and refined in consultation with the clinical co-investigators and advisors to improve functionality and processes in the clinics involved in the trial (e.g., through drop-down menus) (See supplementary study documents for mock-ups of each of the 3 EPIC templates). A member of the clinical staff (and not research staff) will be in charge of the creation of the SCP. The specific follow-up care recommended will be informed by ASCO and other relevant guidelines, as well as standards of care in each clinic. The general recommendations will be based on the guidelines as outlined in Table 1, but the clinician completing the form can tailor the specific recommendations based on clinical judgement. As described above, the SCP will either sent to the patient (Arm A) or delivered in an in-person visit conducted by a nurse, nurse practitioner, or physician assistant (Arms B & C).

Table 1: Recommended Follow-up Care and Outcome Measures

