Outcome Measures (Based on NCCN 2013 and ASCO Guidelines)					
TUMOR TYPE	BREAST	COLORECTAL	PROSTATE	Data Collection Timing and Approach	
Stage	Stage I-III	Stage I-III	Stage I-III		
HEALTH SERVICE USE	Recommended Surveillance	Every 3-6 months: H&P exam Annually: Mammography (excluding women with bilateral mastectomy)	Every 3-6 months: H&P exam CEA Annually: CT scan chest, abdomen, and pelvis Colonoscopy (ok to do first at year 3 if preoperative full colonoscopy normal)	Every 6-12 months: H&P exam PSA	
Patient reports assessed at: Baseline & Months 6, 12, 18
 
Medical records abstracted at: Month 18
 
All health service use variables will be based on medical record abstractions, guided by patient tracking tools. During the study contacts, we will obtain patients' reports of providers they have seen, tests they have undergone, etc. At Month 18, we will obtain & abstract all relevant medical records.

	Not Recommended Surveillance (assumes normal H&P and normal recommended surveillance)	Imaging Breast MRI FDG PET/CT CT chest, abdomen, pelvis Liver ultrasound Bone scan Blood tests Tumor marker CEA, CA15-3, or CA27-29	Imaging Chest X-ray FDG PET/CT	Imaging FDG PET/CT Bone scan	
	Recommended Preventive Care Measures	Visit with primary care provider Annual influenza immunization			

The general recommendations will be based on Table 1, but the clinician completing the form can tailor the specific recommendations based on clinical judgement. As described above, the SCP will either be sent to the patient (Arm A) or delivered in an in-person visit conducted by a nurse, nurse practitioner, or physician assistant (Arms B & C).

For all arms, participants will be followed for 18 months, or until cancer recurrence. The participants will be contacted approximately 6, 12, and 18 months after the end of treatment to provide data on health service use and patient-reported outcomes.

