Health service use will be collected from patient-report via telephone or in-person at 6, 12, and 18 months after completion of treatment, as well as from medical records. Patients will be supplied with a calendar and asked to note office visits, hospitalizations, emergency department visits, prescriptions, tests, and other health resource use. We will also provide participants with a tip sheet for tracking providers visited, care received, tests done, and prescriptions obtained. The tip sheet template has been adapted from the Medical Expenditure Panel Survey, courtesy of the Agency for Healthcare Research & Quality (see study supplemental documents) (Cohen, et al., 1996). At each data collection point, patients will use these resources to report what health services they have received during the past 6 months.

We will also request and abstract the medical record of each participant for the 18-month study period. The abstraction will focus specifically on surveillance and preventive care. We will also collect all health service use during the study period (outpatient visits, tests, imaging studies, hospitalizations, emergency department visits, medication list). These data will allow us to explore receipt of other preventive and screening services that may be age-based and/or not required on an annual basis (e.g., cholesterol screening, cervical cancer screening), as well as overall health service use (see supplemental study documents for Health Services Use document) .

Patient-reported outcomes will be collected at baseline, 6, 12, and 18 months. The default mechanism for these contacts will be via a REDcap form, with a link sent to the participants via email (see supplemental study documents for Pro Data Collection form). Where this is not possible, the research staff will collect data on the telephone, by mail or in-person.

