- Assessment of Survivor Concerns (ASC): The Assessment of Survivor Concerns is a 5-item questionnaire that assesses two subscales: cancer worry and general health worry. Each item is rated on a 4-point scale from 1=not at all to 4=very much. Subscale scores and an overall score are calculated by summing the relevant items. The ASC was developed by Gotay & Pagano and used in a previous study of survivorship care planning (Gotay, C. C., & Pagano, I. S., 2007; Hershman, D. L., et al., 2013).
- Follow-up Care Use among Survivors (FOCUS)-Information Needs Module: The FOCUS information needs questionnaire asks about the need for information regarding 12 topics (Kent, E. E., et al., 2012) Response options are “no,” “yes,” and “not sure.” It was developed by the National Cancer Institute based on previously published information needs questionnaires (Beckjord, E. B., et al., 2008; Mallinger, et al., 2005; Nelson, et al., 2004). The FOCUS study included an evaluation of the impact of survivorship care plans on information needs.

The PROs will be collecting using REDCap (see supplemental study documents). Patients who do not complete the PROs electronically prior to the health-service use follow-up phone calls will have the opportunity to complete the PROs over the phone, by mail, or in-person.

c. Statistical plan including sample size justification and interim data analysis.

No interim analyses are planned.

SAMPLE SIZE: We will recruit 250 participants through JHMI and 125 participants at PRMC oncology program practices (see Table 2). This weighting of recruitment reflects the difference in the number of patients seen at each site, and the fact that we will be studying three separate clinical settings within a large academic center versus a rural based community cancer program. Based on 2011/2012 cancer registry data from each site, our desired sample size is feasible based on approximately 680 breast, 676 colorectal, and 1310 prostate cancer cases newly seen per year at JHMI, and approximately 187 breast, 96 colorectal, and 206 prostate cancer cases newly seen per year at PRMC. To ensure balanced randomization between the three arms, we will stratify by site (JHMI or PRMC) and by cancer type (breast, prostate, or colorectal).

Table 2: Recruitment by Site

Sites	JHMI N=250			PRMC Oncology Program Practices N=125		
Tumor Groups	Breast (n=100)	Colorectal (n=50)	Prostate (n=100)	Breast (n=50)	Colorectal (n=25)	Prostate (n=50)
Arm A	34	17	33	17	8	17

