Arm B	33	16	34	17	8	16
Arm C	33	17	33	16	9	17
Total	100	50	100	50	25	50

Previous studies show that patient adherence in the survivorship period is varied, depending on the cancer type and/or the particular health service being studied. We considered a range of adherence probabilities and varying differences between them among randomization arms. The operating characteristics of the design are shown in Table 3 below. Simulations (1,000) with varying values of the underlying probability of perfect adherence for each study arm provided the estimates in the table. For each simulation, responses for the primary endpoint were randomly drawn from a binomial distribution and compared between study arms with Fisher's exact test. Estimated power is the proportion of simulations that yielded a two-sided p value ≤ 0.05 . Table 3 shows that the study will have more than 80% power to detect differences ranging of about 5% and higher in the proportion of patients with perfect adherence among study arms. Table 3 also shows the power assuming 20% attrition, and even then, we have 80% power to detect differences of 10%-15% (and in some cases lower).

Table 3: Power Calculations for Primary Outcome

Total Sample Size (A / B / C)	Probability of receipt of outcome			Difference between arms	Estimated Power with Type I error = 5%
	Arm A	Arm B	Arm C		
125 / 125 / 125	30%	39.5%	49%	9.5%, 9.5%	79.2%
		37.5%	52.5%	7.5%, 15%	93.2%
		45%	60%	15%, 15%	99.7%
	50%	55%	70%	5%, 15%	88.1%
		65%	72.5%	15%, 10%	91.7%
		65%	80.0%	15%, 15%	99.7%
	70%	75%	87.5%	5%, 12.5%	91.6%
		77.5%	90%	7.5%, 12.5%	96.8%
		82.5%	92.5%	12.5%, 10%	99.3%
Total Sample	Probability of receipt of			Difference	Estimated

Size (A / B / C)	outcome			between arms	Power with Type I error = 5%
	Arm A	Arm B	Arm C		
100 / 100 / 100	30%	39.5%	49%	9.5%, 9.5%	68.7%
		37.5%	52.5%	7.5%, 15%	84.2%
		45%	60%	15%, 15%	98.8%
	50%	55%	70%	5%, 15%	78.7%
		65%	72.5%	15%, 10%	84.8%
		65%	80.0%	15%, 15%	98.5%
	70%	75%	87.5%	5%, 12.5%	82.2%
		77.5%	90%	7.5%, 12.5%	91.6%
		82.5%	92.5%	12.5%, 10%	97.7%

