DATA ANALYSIS: Comparing the three models of SCPs, we will examine whether there are differences between intervention arms in receipt of care as recommended on the SCP, regardless of whether the SCP was received ('intention to treat'), and also whether receipt of an SCP leads to appropriate care receipt, comparing those who received a SCP to those who did not. In both cases, the endpoint is the proportion of patients who receive all cancer-related follow up care. We will also examine each component of appropriate care individually (e.g., proportion receiving mammogram). Analysis will be by Fisher's exact test for differences between groups. To help quantitatively describe the differences between groups, we will also use binary or categorical logistic regression models as appropriate to estimate odds ratios with 95% confidence intervals. To account for the stratified randomization, we will also include a regression model that estimates the main SCP-type effect while adjusting for cancer type and recruitment site. Planned

subgroup analyses include examining differential outcomes by patient cancer type and recruitment site using interaction analyses. P-values for determining statistical significance of these interaction tests will be corrected for multiple comparisons using a Bonferroni approach.

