Receipt of primary/preventive care, avoidance of non-recommended care, and PROs are secondary endpoints, and the analyses are descriptive. The analysis for receipt of primary/preventive care is similar to that for cancer-related follow-up. The endpoint for the avoidance of non-recommended care will be the proportion of patients who do not receive tests that are not recommended in the year following completion of acute treatment. This will be evaluated as a dichotomous variable (did not receive inappropriate care: yes vs. no). For the patient-reported outcomes, we will report the PRO scores by intervention arm at baseline, 6-month, 12-months, and 18-months. The main PRO analysis will be a comparison of the follow-up scores at 12-months by intervention arm adjusting for baseline. We will also compare the PROs at 6 months for Arms B&C vs. Arm A to evaluate the effective of the in-person transition visit vs. just sending the SCP. For the PLANS, we will report mean (SD) scores at the individual item level. For the ASC, we will primarily report the mean (SD) on the two subscale scores, but will also report the individual items and total score. For the FOCUS Information Needs, we will primarily report total number of health information needs (i.e., number of items endorsed “yes”), but will also report individual needs endorsed (dichotomous). For all of the PROs, we will also explore changes longitudinally using appropriate methods (GEE, random effects) and examine any differences in the trends over time between patient subgroups using interaction tests as needed.

d. Early stopping rules.

Early stopping rules are not applicable to this study.

8. Risks

a. Medical risks, listing all procedures, their major and minor risks and expected frequency.

There is a risk of participants feeling tired, bored, or uncomfortable when answering questions about health and health care.

b. Steps taken to minimize the risks.

Participants do not have to answer any question they do not want to answer.

c. Plan for reporting unanticipated problems or study deviations.

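### Table 1 schedules a baseline report of health service use that the text omits and no analysis uses, so the preventive-care comparison may be somewhat less precise than it could be

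*Combined protocol and SAP*

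**What the plan says.** **Schedule.** Table 1 (Section 4, STUDY IMPLEMENTATION) has a column for timing and method of data collection. Against the health-service-use rows it reads "Patient reports assessed at: Baseline & Months 6, 12, 18", with record abstraction at month 18. The service-use paragraph that follows the table says "Health service use will be collected from patient-report via telephone or in-person at 6, 12, and 18 months after completion of treatment", plus medical records. A later paragraph in the same section gives patient-reported outcomes (PROs) a baseline as well as months 6, 12 and 18. Section 4.b makes the same split: service use at 6, 12 and 18 months, PROs at baseline and those months.

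**Content of the reports.** Each service-use report covers the preceding six months. Records are abstracted for the 18-month study period, and no earlier window is stated.

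**Outcome and analysis.** Preventive care is a yes/no secondary outcome (Section 7.b). Its two services in Table 1 are a primary care visit and annual influenza immunization. Section 7.c, DATA ANALYSIS, says: "The analysis for receipt of primary/preventive care is similar to that for cancer-related follow-up". That means Fisher's exact test, logistic odds ratios with 95% confidence intervals, and a regression model that "estimates the main SCP-type effect while adjusting for cancer type and recruitment site". The same section calls the secondary analyses descriptive. PROs are adjusted for their baseline value; service use is not.

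**The concern.** Staff cannot tell from the protocol whether to ask about service use at baseline. If they follow Table 1, a report is collected that no analysis uses. If they follow the text, no planned source describes use before enrolment, because record abstraction covers only the study period.

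A patient's earlier use of the same recurring services is a natural candidate predictor of later use. The plan accepts the principle for PROs but does not extend it to preventive care. What is at stake is the width of the confidence intervals for one named secondary outcome of Aim 1.

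**Working it through.** **1. Inputs from the documents.**
- Allocation: "We will use stratified randomization to assign enrolled patients 1:1:1 to the 3 study arms".
- Size: "We will recruit 250 participants through JHMI and 125 participants at PRMC oncology program practices", so 250 + 125 = 375, or 125 per arm. With 20% attrition, Table 3 uses 100 per arm.
- Test behind Table 3: simulated binomial outcomes "compared between study arms with Fisher's exact test"; "Estimated power is the proportion of simulations that yielded a two-sided p value ≤ 0.05".

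**2. Inputs that are assumptions.** The documents give no receipt rates for preventive care and no association between earlier and later use. I borrow receipt rates from Table 3, which concerns the primary outcome, and vary phi, the correlation between prior use (yes/no) and the outcome (yes/no), from 0.1 to 0.5.

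**3. Reproducing the plan's own figures.** Re-simulating the three-arm Fisher test with 10,000 runs per row puts 17 of the 18 rows of Table 3 within 2 points. For 30/39.5/49%, 79.2% is stated at 125 per arm and 79.3% found; at 100 per arm, 68.7% and 69.4%. The exception is 50/55/70% at 125 per arm: 88.1% stated, 86.0% found. The standard error of a 1,000-run estimate is about √(0.88 × 0.12 / 1,000) = 1.0 point, so a gap of 2.1 points is about two standard errors and not evidence of an error.

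**4. Power with adjustment (large-sample approximation).** The noncentrality is λ = n Σ(pᵢ − p̄)² / [p̄(1 − p̄)] on 2 degrees of freedom. Adjustment for prior use divides λ by (1 − φ²). For 30/39.5/49% at 125 per arm, p̄ = 0.395 and λ = 125 × 0.01805 / 0.238975 = 9.44, which gives 79.1%. At φ = 0.3, λ = 9.44 / 0.91 = 10.4, which gives 83.0%. At φ = 0.5, λ = 9.44 / 0.75 = 12.6, which gives 89.8%.

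**5. Precision.** The pairwise 95% half-width at a 50% rate is 1.96 × √(2 × 0.25 / 125) = 12.4 points. Adjustment multiplies it by √(1 − φ²). The equivalent number per arm is 125 / (1 − φ²).

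| φ | Half-width, points | Narrower by | Equivalent n per 125 | Power, 30/39.5/49%, n = 125 | Same rates, n = 100 | Power, 50/55/70%, n = 100 |
|---|---|---|---|---|---|---|
| 0 | 12.4 | – | 125 | 79.1% | 69.1% | 76.6% |
| 0.1 | 12.3 | 0.5% | 126 | 79.6% | 69.6% | 77.1% |
| 0.2 | 12.1 | 2% | 130 | 80.9% | 71.0% | 78.4% |
| 0.3 | 11.8 | 5% | 137 | 83.0% | 73.4% | 80.7% |
| 0.4 | 11.4 | 8% | 149 | 86.1% | 77.0% | 83.9% |
| 0.5 | 10.7 | 13% | 167 | 89.8% | 81.8% | 88.0% |

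**6. Check by simulated logistic models.** These use likelihood-ratio tests of arm with and without the covariate, 1,500 runs and 50% prior use. For 30/39.5/49% at 125 per arm, power rises from 79.7% to 83.5% at φ = 0.3 and from 78.7% to 89.5% at φ = 0.5. This agrees with step 4 within simulation error.

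**7. What a given φ requires.** Let g be the difference in receipt between prior users and non-users, q the prevalence of prior use and r overall receipt. Then φ² = g² q(1 − q) / [r(1 − r)]. At r = 50%:
- g = 50 points, q = 50%: 0.25 × 0.25 / 0.25 = 0.25, so φ = 0.5 and the gain is worth 1/0.75, about 33% more patients.
- g = 50 points, q = 80%: 0.25 × 0.16 / 0.25 = 0.16, so φ = 0.4 and about 19% more patients.
- g = 30 points, q = 50%: φ² = 0.09. At q = 80%, it is about 0.06.

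For a given g and r, q = 50% is therefore the most favourable case.

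**The case against.** The strongest reply is that nothing in the analysis is wrong. Leaving a prognostic covariate out of a randomised comparison does not bias it, a model with both stratification factors is already planned, the outcome is secondary and descriptive, and no power is claimed for it. All of that stands. It limits the point to precision, but the plan still calls for odds ratios with confidence intervals, and their width is what limits a descriptive estimate.

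A reader might go further and infer that precision is being thrown away on data already scheduled. The documents do not support that. Table 1 does not say what the baseline report asks. The only stated recall is six months, which can miss an annual immunization, so the 12-month questions proposed below are new. The supplemental forms, which I have not seen, may settle the content.

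Nor is the benefit assured. Enrolment comes around the end of acute treatment, so a 12-month look-back will often overlap that treatment, when use may be untypical. The documents contain nothing on how well it predicts later use.

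The conflict should not be overread either. The months given in Section 4.b follow a sentence about follow-up data. The contact schedule just below Table 1 also covers PROs, which do have a baseline. Neither clearly excludes a baseline service-use report. The clear mismatch is the service-use paragraph after Table 1. Finally, nothing shows that earlier entries could not be obtained from the medical records; it is only that no such abstraction is planned.

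**Conclusion.** The point holds in a limited form. Table 1 and the text disagree on a baseline report of service use, and the plan gives that report no analytic role. Adjusting preventive care for prior use would bring a gain from negligible (φ of 0.1 to 0.2: 0 to 2 power points, intervals 0.5 to 2% narrower) to moderate (φ of 0.3 to 0.5: intervals about 5 to 13% narrower). In the three power columns tabulated, the moderate range corresponds to roughly 4 points at φ = 0.3 and 11 to 13 points at φ = 0.5. These figures rest on an assumed φ and on receipt rates borrowed from the primary outcome.

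Three stronger conclusions might be inferred and are not supported. The comparison is not biased. Table 3 is not affected, since it concerns the primary outcome. There is also no case for replacing Fisher's exact test, which cannot take covariates, or for adding these covariates to the cancer follow-up model, because nothing shows that a primary care visit or influenza immunization predicts cancer surveillance.

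**What to change.** 1. Keep the baseline service-use report as in Table 1, and make Section 4.b, the text below Table 1 and the service-use paragraph agree with it.
2. Have the report record a primary care visit and influenza immunization (yes/no each) over the previous 12 months. Because the arms are not blinded, ask before the patient learns the allocation.
3. In Section 7.c, add prior use, with cancer type and site, to the adjusted logistic model already planned for preventive care and for each of its two components.
4. Report standardised proportions or risk differences beside the odds ratios, because odds ratios adjusted for a prognostic covariate are conditional and not comparable with unadjusted ones.
5. Leave Fisher's exact test and the primary cancer follow-up model unchanged.

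The cost is two questions at a baseline contact that already exists and is already paid ($25, Table 5), plus a few lines of text. The downside is that the gain may be small if use during acute treatment predicts later use poorly.

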We will also compare relevant patient-reported outcomes (PROs) across the three intervention arms (secondary outcomes). We will assess knowledge about and confidence in follow-up care using the Preparing for Life as a (New) Survivor (PLANS); cancer worry and health worry with the Assessment of Survivor Concerns (ASC); and information needs with the Follow-up Care Use among Survivors (FOCUS) questionnaire.

AIM 3: Assess patients' perspectives on the value of survivorship care planning

We will conduct qualitative interviews with a subset of patients (n=40) to assess which aspects of the SCP process are most valued and explore whether there are different perspectives on the value of SCPs between institutions or by cancer type or study arm. This aim is not included in this protocol. It will be submitted as an amendment as the interview guide will be informed by the implementation of the trial.

Data from the 3 aims will identify attributes of SCP models and implementation processes that can be used to promote feasible and effective patient-centered survivorship care planning processes across a range of clinical settings, cancer types, and populations served. Determination of the preferable mode of SCP delivery will be based off of the primary endpoint (receipt of recommended follow-up care over 18 months).

3. Background (briefly describe pre-clinical and clinical data, current experience with procedures, drug or device, and any other relevant information to justify the research)

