OVERVIEW: The primary aim of this trial is to assess whether there is a difference among three SCP models of varying levels of resource intensity and patients' receipt of recommended health services in the months following completion of acute treatment. We will conduct a randomized controlled trial (RCT) to measure whether the provision of the SCP to the survivor and PCP is associated with survivors' receipt of cancer follow-up care as outlined on their SCP (primary outcome). Avoidance of non-recommended care, receipt of recommended primary and preventive care, and patient-reported outcome measures will serve as secondary endpoints.

Participants in the RCT will have been treated for breast, prostate, or colorectal cancer. This RCT will be conducted in four oncology clinics in two medical systems. We will enroll survivors of Stage I-III breast, prostate, or colorectal cancer who are completing treatment and transitioning to long-term survivorship, and use a stratified randomization to assign participants to one of three study conditions (Arms A, B or C). This study will focus specifically on the period following completion of acute treatment (e.g., surgery, radiation, and chemotherapy); patients receiving long-term adjuvant endocrine/antibody therapies will also be eligible.

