Patient participants randomized to Arm C will receive a copy of the SCP during an in-person ‘stethoscope free’ visit with a nurse, nurse practitioner, or physician assistant. A copy of the SCP will be added to the medical record and a copy will be sent to the primary care provider on record. The visit will be scheduled after consent is signed and will occur within approximately 3 months after treatment completion. The initial visit will focus on review of the SCP content and offer an opportunity for patients to ask questions about any aspect of the plan or associated treatment and survivorship issues. In addition, patients randomized to Arm C will receive a follow up survivorship visit approximately 6 months after the initial in-person ‘stethoscope free’ visit. The follow-up visit will focus on a review and refresher of the SCP and offer patients the opportunity to ask about any persistent or emerging issues.

- c. Blinding, including justification for blinding or not blinding the trial, if applicable.

Given the nature of the interventions, it is not possible to blind patients or providers to the randomization arm.

- d. Justification of why participants will not receive routine care or will have current therapy stopped.

All patients will receive routine care and there is no impact on current therapy. This study is evaluating three different approaches for survivorship care planning, each of which is standard of care.

- e. Justification for inclusion of a placebo or non-treatment group.

Because of the Commission on Cancer Accreditation requirement that all cancer patients completing acute treatment receive a survivorship care plan, a no intervention arm is not appropriate. Rather, this study will

evaluate different approaches for conducting survivorship care planning in the simplest way that is still effective in helping survivors receive appropriate follow-up care.

f. Definition of treatment failure or participant removal criteria.

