- Not treated with intent to cure;
- Did not have cancer care primarily managed within one of the 4 participating clinics, or JHMI or PRMC oncology program practices are not primarily responsible for the patients’ survivorship care;
- Does not have health insurance at screening; and
- Enrolled in a competing and/or conflicting research trial at the time of enrollment.

6. Drugs/ Substances/ Devices

Not applicable

7. Study Statistics

a. Primary outcome variable.

The primary endpoint of this study will be the proportion of patients who receive appropriate cancer-related follow-up care (based on the individual's SCP). The outcome will be operationalized as a dichotomous variable (received recommended care: yes/no). This endpoint will be used to determine the preferable delivery modality (study arm).

b. Secondary outcome variables.

Secondary outcomes of health service use include (1) receipt of appropriate primary and preventive care and (2) not receiving tests that are not recommended. These outcomes will also be operationalized as a dichotomous variable (received recommended primary/preventive care: yes/no; did not receive inappropriate care: yes/no). In addition to the dichotomous outcomes, we will also examine receipt of individual care services. For example, the primary dichotomous outcome for colorectal cancer patients may include receipt of colonoscopy and CEA testing; as a secondary outcome, we will also examine receipt of each of those services separately.

Patient-reported outcomes (PROs) are also important secondary outcomes. Participants will complete PRO measures assessing survivorship knowledge and confidence, worry, and information needs at baseline, 6-months, 12-months, and 18-months post treatment completion. Based on a review of the literature and consultation with the survivor members of our Stakeholder Advisory Board, the PRO assessment will include three instruments:

- Preparing for Life as a (New) Survivor (PLANS): The PLANS survey includes 11 knowledge items rated on a 4-point Likert scale from 1=strongly disagree to 4=strongly agree, as well as 5 confidence items rated on a 10-point scale from 1=not at all confident to 10=extremely confident, and an open-ended question. The PLANS was developed at the University of Michigan and was used by our team in a previous survivorship care planning evaluation (Dunn, R., Crowley, S., & Janz, N., 2011; Smith et al., 2016). The items are analyzed individually.

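### The primary endpoint is to decide the preferable arm, but no arm contrasts, naming rule or cross-arm error control are pre-specified, and Table 3 gives three-group power only

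*Combined protocol and SAP*

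**What the plan says.** The commitment to choose an arm appears twice. Section 2 (Objectives) states: "Determination of the preferable mode of SCP delivery will be based off of the primary endpoint". Section 7.a, having defined the primary endpoint as a yes/no variable, adds: "This endpoint will be used to determine the preferable delivery modality (study arm".

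The overview in section 4.a words the primary aim differently, as a global question: to "assess whether there is a difference among three SCP models". Section 4.e describes the purpose as evaluating ways of doing survivorship care planning "in the simplest way that is still effective".

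The analysis is in section 7.c under Data Analysis: "Analysis will be by Fisher's exact test for differences between groups". To describe group differences, "we will also use binary or categorical logistic regression models as appropriate to estimate odds ratios with 95% confidence intervals". A further regression carries cancer type and site as covariates. The only multiplicity provision concerns subgroups: "P-values for determining statistical significance of these interaction tests will be corrected for multiple comparisons using a Bonferroni approach".

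Table 3 (section 7.c, Sample Size) gives simulated power for nine sets of A/B/C rates, at 125 and at 100 per arm, using Fisher's test at two-sided 5%. The accompanying text claims power above 80% for gaps from roughly 5 points upward.

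The one between-arm contrast that the plan names is B and C together against A, for the secondary patient-reported outcomes at 6 months.

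**The concern.** A significant test that three proportions are not all equal does not say which arms differ. Calling one arm preferable needs contrasts between arms, a rule for reading them, and control of the chance of a false claim over three comparisons. The plan supplies these elsewhere (a named contrast for the 6-month patient-reported outcomes, Bonferroni for interactions) but not for the decision that the trial exists to inform.

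The arms rise in intensity, and section 8.e says that participants in Arms B and C bear copays for one or two visits. The steps that matter for the decision are therefore B vs A and C vs B. If the contrasts and rule are left until the data are seen, the choice of arm becomes post hoc. Table 3 may also lead readers to think that these steps are well powered.

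**Working it through.** **Inputs.** 1:1:1 allocation; 125 per arm, or 100 after 20% attrition; two-sided 5%; Fisher's exact test; rates from Table 3.

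**Step 1: reproduce Table 3.** Each scenario was simulated 6,000 times with one 3×2 exact test, rejecting at p ≤ 0.05.

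| A/B/C (%) | Stated, 125 | Reproduced | Stated, 100 | Reproduced |
|---|---|---|---|---|
| 30/39.5/49 | 79.2 | 78.9 | 68.7 | 69.9 |
| 30/37.5/52.5 | 93.2 | 92.2 | 84.2 | 84.4 |
| 30/45/60 | 99.7 | 99.5 | 98.8 | 97.7 |
| 50/55/70 | 88.1 | 87.1 | 78.7 | 77.9 |
| 50/65/72.5 | 91.7 | 92.6 | 84.8 | 85.6 |
| 50/65/80 | 99.7 | 99.6 | 98.5 | 98.9 |
| 70/75/87.5 | 91.6 | 90.3 | 82.2 | 82.1 |
| 70/77.5/90 | 96.8 | 97.0 | 91.6 | 92.0 |
| 70/82.5/92.5 | 99.3 | 99.2 | 97.7 | 97.6 |

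The largest gap is 1.3 points, so the table is the power of a single three-group test. One label needs care: the 50/65/72.5 row gives its B–C gap as 10%, but 72.5 − 65 = 7.5. With 75% in Arm C the three-group power would be 96.9%, so the stated 91.7% belongs to 72.5%, which is used below.

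**Step 2: power per pair.** Exact power = Σ Bin(x; n, p₁) · Bin(y; n, p₂), summed over all (x, y) for which the two-sided 2×2 Fisher p-value is ≤ 0.05.

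| Pair (%) | 125 per arm | 100 per arm |
|---|---|---|
| B vs A, 50 vs 65 | 61.9% | 53.0% |
| C vs B, 65 vs 72.5 | 20.9% | 16.7% |
| C vs A, 50 vs 72.5 | 94.6% | 88.4% |
| 30 vs 45 | 64.7% | 53.5% |
| 45 vs 60 | 61.5% | 53.0% |
| 55 vs 70 | 64.7% | 53.5% |
| 65 vs 80 | 71.9% | 60.8% |
| 50 vs 55 | 9.9% | 9.2% |
| 70 vs 75 | 11.4% | 9.4% |

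Cross-check for 65 vs 72.5 by the normal approximation. The pooled rate is 0.6875. The null SE is √(2 × 0.6875 × 0.3125/125) = 0.0586, and the SE under the alternative is √((0.2275 + 0.1994)/125) = 0.0584. Power = Φ((0.075 − 1.96 × 0.0586)/0.0584) = Φ(−0.68) ≈ 25%. Fisher's test is conservative, which accounts for 21%.

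So Table 3's adjacent 15-point pairs have about 61–72% power at 125 per arm and 53–61% at 100. The two 5-point pairs sit in rows stated at 88.1% and 91.6%. Those powers come mainly from the A–C spreads of 70 − 50 = 20 and 87.5 − 70 = 17.5 points.

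**Step 3: naming Arm C.** In the 50/65/72.5 row at 125 per arm, the three-group test is significant while C vs B is not in about 72% of trials. Over the nine rows, the simulated power to show C better than both other arms, with pairwise tests run only after a significant three-group test, is 21–73%. Table 3 states 79.2–99.7%.

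**Step 4: false claims with all rates at 50%.** The chance that at least one of three unadjusted pairwise Fisher tests is significant is 9.2% at 125 per arm and 10.0% at 100. Requiring a significant three-group test first brings it to 4.8% at both sizes.

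**Step 5: the three-group test read alone.** For illustration, assume 50/65/65 at 125 per arm; this is not a Table 3 row. The three-group test is significant in 69.8% of trials. Among these, B is nominally best in 47.6%, C in 47.6%, and they tie in the remaining 4.8%, although they are equal.

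**The case against.** The aim in section 4.a is global, and a three-group test with three-group power answers it. That stands: the mismatch lies only with the sentences in sections 2 and 7.a that promise a choice of arm.

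Section 7.c never says that the test is three-group only; that follows from reproducing Table 3. The plan also provides odds ratios with intervals and an adjusted model, and these bear on which arms differ. This stands too. They do not close the gap, because no reference arm or contrast is named, the odds ratios are there for description, and neither analysis has a role in the decision.

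The per-pair figures should not be read one-sidedly. In the 50/65/72.5 row C vs A is well powered, and C, the truly best arm, is nominally highest in about 89% of significant trials. In the 50/65/65 illustration either B or C is a correct choice on the primary endpoint; the loss is an unneeded visit and its copay.

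A reader might infer that the plan selects whichever arm has the highest observed proportion, or that it would take a null result as showing that the simplest arm suffices. Neither rule is written. Both are risks of silence, not stated procedure.

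**Conclusion.** The gap is real and should be closed before analysis. The plan promises to name a preferable arm without stating contrasts, a naming rule or error control across arms, and its power table answers a different question. On one reading of section 7.c (unadjusted pairwise tests) the family-wise error is about 9–10% at rates of 50%; on the other (the three-group test alone) a significant result does not locate the difference. Either reading needs the same repair.

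The sentence on power for differences of about 5% is not supported for any pair of arms that far apart, where power is about 10–11% at 125 per arm. The first 125-per-arm row, with 9.5-point steps, is itself stated at 79.2%.

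It would go too far to say that the trial cannot support a choice of arm. The three-group test is held at 5%, and with exactly three arms a pre-specified pairwise step behind it is valid at no cost in alpha. The figures assume Table 3's rates, full arms of 125 or 100 and unadjusted Fisher tests per pair. Gating changes them little: in the 50/65/72.5 row, C vs A falls from about 95% to 92%.

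**What to change.** Add to section 7.c:

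- Run the three-group Fisher test at two-sided 5%. Only if it is significant, test B–A, C–A and C–B, each at 5%. With three arms, any two pairwise equalities imply that all three are equal, so this is a closed procedure and controls family-wise error.
- Report all three risk differences with 95% intervals. Near 50% the half-width at 125 per arm is 1.96 × √(2 × 0.25/125) = 12.4 points.
- Call one arm preferable to another only if that contrast is significant, and accept that no single arm may be identified.
- State that a non-significant result is not evidence that a simpler arm is as good. No margin is given, so the plan cannot show that as it stands.
- Label Table 3 as three-group power, put per-pair power beside it, and correct the 5% sentence.

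Holm or a fixed sequence would also control the error; what matters is fixing one procedure in advance. The cost is some text, three contrasts and an extra set of power figures. The stated power for choosing between arms will be lower than Table 3 suggests. No extra patients are needed.
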